5.6. Safety Endpoints

No safety endpoints are being collected for this study.

6. HANDLING OF MISSING VALUES

Subjects with missing values for a particular endpoint will not contribute to the analysis of that endpoint. Missing data will not be imputed.

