8.7. Data Analysis

Detailed methodology for summary and statistical analyses of data collected in this study will be documented in a Statistical Analysis Plan (SAP), which will be dated, filed and maintained by the sponsor. The SAP may modify the plans outlined in the protocol; any major modifications of primary endpoint definitions or their analyses would be reflected in a protocol amendment.

All analyses are to be descriptive and so all methods to be used will reflect this descriptive nature. The specific method that will be used depends on type of variable being analysed and those methods are:

- Categorical variables – will be described using:
 - Number of observations (n);
 - Number and percent (%) within each category;
 - Number of missing observations.
- Numeric variables – will be described using:
 - Number of observations (n);
 - Mean and Standard deviation;
 - Minimum, Maximum, Median and 1st and 3rd Quartiles;
 - Number of missing observations.
- Time to event – will be described using:
 - A Kaplan-Meier chart that will visually estimate the distribution of times to some events, eg, progression, and will take into account those patients for which the event has not as yet occurred;
 - 1-yr and 2-yr rates, median or some more appropriate percentiles if the median time is not reached in the sample.

The analyses will be conducted (using the methods above) in a number of phases, as already detailed in the study design section.

1. Non EU countries – all variables (as shown in [Section 8.3](#)) will be described.

2. EU countries – selected variables (all shown in [Section 8.3](#) excluding clinical outcomes) will be described.
3. EU countries - all variables will be described.

Missing data will be excluded on a case by case basis and will not be imputed. This will mean that each table will not necessarily be based on the same number of patients.

Subgroup Analysis

Exploratory stratifications will be conducted to explore differences between line of therapy, demographics, treatments, clinical characteristics, baseline co-morbidities or ‘responders’ and ‘non-responders’ to treatment, however these will be only descriptive in nature. Responders and non-responders will be defined according to the best recorded response to palbociclib treatment.

Sample size permitting, additional stratifications may include:

- Insurance type.
- Eastern Cooperative Oncology Group (ECOG) Performance status.
- Age.
- Menopausal status.
- De novo vs. recurrent disease.

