8.8. Quality Control

To maximize data quality the following will be undertaken:

- Provision of standardized instructions on study design, methodology and procedures:
 - Physicians will be contacted via email or telephone and an overview of the study will be provided (detailing study objectives, patient inclusion criteria, correct completion of eCRF and interview and any other logistical aspects of the study);
 - Follow-up with the physicians to ensure queries are resolved quickly.
- The electronic materials will be tested thoroughly to ensure that all questions appear correctly on screen, allow easy interpretation/completion and that all routing and logic checks are working correctly. As such, there should be no missing data (given the online nature of the study, the physician will have to complete a question before he/she is able to move on the next) however, ‘don’t know or unknown’ will be valid responses.
- There will be no monitoring visits or source data verification in this study.

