5.2. Patient Characteristics

To be abstracted directly from the medical records:

- Dead/alive at date of record abstraction;
- Time since death (if applicable);
- Ethnicity;
- Age at palbociclib initiation;
- Menopause status;
- Type of menopause (natural or induced);
- Insurance plan (vary according to country eg, Medicare, Medicaid, Commercial, None).

To be Derived:

- Age at initial breast cancer diagnosis;
- Age at ABC/mBC diagnosis.

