- Survival at 12, 18, 24 months defined as the proportion of patients who are not deceased at defined time points.

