Number of interruptions	Primary objective 4	CRF H3b	Including zeros, ie, no interruptions
Duration of interruptions	Primary objective 4	CRF H3a	
Any cycle delays?	Primary objective 4	CRF H3b	
Duration of cycle delays	Primary objective 4	CRF H3a	
Reasons for dose change	Primary objective 4	CRF H3c	Multiple responses allowed. Reduce to patient level, ie, if “lack of response” is ticked for any dose changes then “lack of response” is considered ticked
Status of combination partner therapy when dose is changed	Primary objective 4	CRF H3d	
Time from palbociclib initiation to first dose change	Primary objective 4	CRF H3a	

Table 5. Supportive Therapies Whilst Receiving Palbociclib

Variable	Role	Data source(s)	Operational definition
All supportive therapies received whilst receiving palbociclib	Primary objective 5	CRF H4	Multiple responses allowed

Table 6. Clinical Outcomes

Variable	Role	Data source(s)	Operational definition
CCI			
Progression free survival	Exploratory objective	CRF G2e	Defined as the time from the start of palbociclib to the first subsequent progression or death. The treatment grid in section G will be used to determine in which treatment line that this occurs.
Progression free at 6, 12, 18, 24 months of treatment	Primary objective 6	CRF G2e	Proportion of patients who have not displayed progression at defined time points.
Did the patient achieve complete response whilst receiving palbociclib?	Primary objective 6	TBC	
Time to complete response	Primary objective 6	TBC	
Did the patient achieve partial response whilst receiving palbociclib?	Primary objective 6	TBC	
Time to partial response	Primary objective 6	TBC	
Objective Response Rate	Primary objective 6	CRF I1d/I1e	Proportion of patients who achieve CR/PR at CRF I1d/I1e.

Variable	Role	Data source(s)	Operational definition
Time to Death	Primary objective 6	CRF B7	This will be the time from the start of palbociclib to death. This will only include patients for whom death has been recorded.
CCI			
Survival at 12, 18, 24 months	Primary objective 6	AQ2, BQ7	Proportion of patients who have not died at defined time points.

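### SAP section 6 would drop a recorded death with no known date from the 12-, 18- and 24-month survival estimates, which pushes survival upward if such deaths occur

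*SAP*

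**What the plan says.** **Missing values.** SAP section 6: "Subjects with missing values for a particular endpoint will not contribute to the analysis of that endpoint", followed by "Missing data will not be imputed". Protocol section 8.7 agrees: "Missing data will be excluded on a case by case basis and will not be imputed".

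**What is collected.** SAP section 5.2 lists "Dead/alive at date of record abstraction" and, as a separate item, "Time since death (if applicable". SAP Appendix 1 takes vital status from BQ6 and the survival landmarks from AQ2 and BQ7. Protocol section 8.8 says the eCRF forces an answer to each question, but "don’t know or unknown’ will be valid responses". It also rules out source data verification.

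**The endpoint.** The clinical outcomes list in SAP section 5.5 has "Survival at 12, 18, 24 months defined as the proportion of patients who are not deceased at defined time points". Appendix 1, Table 6 repeats it as "Proportion of patients who have not died at defined time points". SAP section 7.2 describes death by Kaplan-Meier, with time-point rates read from the life tables.

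Neither document has a rule for a patient recorded as dead whose time since death is unknown.

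**The concern.** An event time is needed to place a death on the survival curve, and only a patient who died can lack it. A living patient contributes her follow-up without any answer to that item. For time since death, whether the value can be missing is therefore decided by the outcome. The complete-case rule can then remove deaths and nothing else, which is not the neutral loss of data that such a rule assumes.

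The proportions alive at 1 and 2 years belong to the primary clinical-outcome objective (protocol section 7, SAP section 3.1). PFS also counts death as an event (SAP section 7.2.1), so an undated death with no earlier dated progression event raises the same problem there. SAP section 7.2 repeats all endpoints by stratum, so if the share of undated deaths differed between strata, the comparisons would shift too.

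**Working it through.** **1. Denominator.** The eCRFs in protocol Table 2 sum to 3131. Removing the German interim review, which collected no clinical outcomes, gives 3131 − 257 = 2874. This reproduces the core figure in SAP section 2.1.1. The documents give no survival rate, death count or share of undated deaths, so there is no other planned figure to reproduce.

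**2. Assumptions (not in the documents).** True 24-month survival *S* is 60, 70 or 80%. A share *m* of deaths is undated, from 5 to 30%, and undated deaths are a random subset of all deaths.

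**3. Closed form with follow-up complete to 24 months.** Dropping a share *m* of the deaths leaves *S* survivors out of 1 − *m*(1 − *S*) patients:

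S′ = S / (1 − m(1 − S))

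For *S* = 0.70 and *m* = 0.10: 0.70 / (1 − 0.10 × 0.30) = 0.70 / 0.97 = 0.722, a shift of +2.2 points.

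| True S at 24 months | m = 0 | m = 5% | m = 10% | m = 20% | m = 30% |
|---|---|---|---|---|---|
| 80% | 80.0 | 80.8 | 81.6 | 83.3 | 85.1 |
| 70% | 70.0 | 71.1 | 72.2 | 74.5 | 76.9 |
| 60% | 60.0 | 61.2 | 62.5 | 65.2 | 68.2 |

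**4. Check with staggered follow-up.** Kaplan-Meier was applied to 400,000 simulated patients per scenario, with exponential survival and abstraction uniform between 3 and 36 months after start. The 3 months is the shorter minimum follow-up in the eligibility criteria; the 36 is assumed. The 24-month shifts for true survival of 80, 70 and 60% were:

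- *m* = 5%: +0.8, +1.1 and +1.3 points
- *m* = 10%: +1.6, +2.1 and +2.5 points
- *m* = 30%: +5.1, +6.9 and +8.2 points

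These agree with the closed form. At *m* = 10% the shift is +0.8 to +1.6 points at 12 months and +1.3 to +2.1 at 18 months. With all deaths kept, Kaplan-Meier returns the assumed survival.

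**5. Scale in patients.** In the simulation 16.3, 24.5 and 32.6% of patients had died by abstraction. Applied to 2874 patients this is about 468, 704 and 937 deaths, so 10% undated would be about 47, 70 and 94 patients.

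**6. Other gaps under the same rule, same simulation, at 24 months.**

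- Start date unknown in 10% of patients regardless of outcome: no material shift.
- Dropping 10% of the patients not dead at abstraction because vital status is unknown: −1.7 to −2.6 points.
- Landmark read as a simple proportion, with living patients of shorter follow-up treated as missing: −13.6 to −17.9 points. With 10% of deaths also undated: −11.4 to −15.6 points.

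**The case against.** **The eCRF is not in the documents.** Protocol section 8.8 speaks of the whole form, and the same sentence expects no missing data. Whether BQ7 itself offers an unknown option cannot be checked, and SAP section 7.2 lists missing and unknown as separate categories. This stands as a limit: the problem is conditional. It does not remove the gap, because an unknown time is unusable in Kaplan-Meier whatever it is called. Censoring such a patient at last contact instead would still lose a known death.

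**A reader might infer that only patients who died can lack what survival needs.** That is true of the death date alone. Survival also needs vital status and the treatment start date, and either can be unknown for any patient.

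**A reader might infer that reported survival is bound to be too high.** The documents do not support this. It takes at least one undated death, and no count is given. The net direction of all missing data is also open: unknown vital status among living patients pulls the estimate down, and the simple-proportion wording, if living patients with short follow-up were dropped, pulls it down further. The Kaplan-Meier method in SAP section 7.2 avoids that last problem, but the plan does not reconcile the two descriptions.

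**A reader might extend the point to Time to Death or to particular countries.** Appendix 1, Table 6 restricts Time to Death to recorded deaths, so dropping some of them does not leave survivors over-represented. Nothing in the documents shows where undated deaths would cluster.

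**The study is descriptive, uses a convenience sample, and reports 1- and 2-year survival only as follow-up and sample size permit.** That lowers the stakes, but it does not justify a rule that can discard known events. Presenting the missing and unknown categories, as SAP section 7.2 requires, would reveal undated deaths but not correct the estimate.

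**Conclusion.** Wrong as written, conditional on undated deaths occurring. SAP section 6 removes a recorded death with unknown time since death from the survival estimates, and no living patient is removed for that item. Under Kaplan-Meier, and considered alone, this component can only move 12-, 18- and 24-month survival upward.

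The plausible size is modest: about 1 to 2.5 points at 24 months with 5 to 10% of deaths undated. It could reach about 8 points at 30% undated with true survival of 60%, though nothing in the documents points to a share that high. With no undated deaths the effect is zero. These figures rest on the assumed survival range and on undated deaths being a random subset of deaths. PFS is affected only for a patient whose undated death has no earlier dated progression event.

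**What to change.** Add an exception to SAP section 6 and align protocol section 8.7:

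- A patient recorded as dead is not excluded from the Kaplan-Meier survival estimates because time since death is unknown. The same holds for PFS when she has no earlier dated progression event.
- Bound her death between the last dated entry in eCRF sections G and H (treatment, progression or dose change) and the abstraction date, and analyse it as interval-censored. The Turnbull estimator does this and reduces to Kaplan-Meier when every death is dated.
- As sensitivity analyses, place all undated deaths at the earliest bound, then all at the latest.
- Report the number of undated deaths by country and stratum.
- State in SAP section 5.5 and Appendix 1, Table 6 that the landmarks are Kaplan-Meier estimates, with living patients censored at last follow-up.

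The cost is a short SAP paragraph, a matching protocol sentence and a small amount of programming on items the eCRF already collects. Fixing deaths at a bound is a limited exception to the no-imputation rule, so both documents must permit it. Reported survival may become slightly less favourable. If there are no undated deaths, the estimates do not change.

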7. STATISTICAL METHODOLOGY AND STATISTICAL ANALYSES

7.1. Data Management

All data and project files will be stored on Adelphi Real World's network which has fail-safe/backup and archive protection.

Stata/SE 14.2 (or higher) on the Windows platform will be used for all analyses.

All statistical tasks are retained in written code (i.e. no menu commands will be utilised), and an overall structure to the code is planned to meet the following requirements:

- All data manipulation steps/analyses performed must be transparent and fully reproducible;
- Analyses should be programmed in sections for ease of interpretation;
- Where possible, programming code should not be hard coded to specific folders/directories;
- Code should be easy to understand to a competent statistician familiar with the programme used.

The starting point for the code will be opening the extracted database export and then a run of any variable cleaning/creation/manipulation commands before analysis steps are taken.

Headings and explanatory comments will be included with the programming code to make clear the purpose of each section. The comments will make it possible for another statistician, skilled in the package used, to fully understand both the programming code and the justifications behind it.

Saving programming code allows for replicability of the analyses at a later date.

7.2. Statistical Methods

Based on the descriptive nature of the study, all study measures will be summarized descriptively through the tabular and graphical display of mean values, standard deviations, and ranges for continuous/numeric variables of interest. For categorical variables, frequency distributions (n, %) will be displayed. Missing and unknown categories for each variable also will be presented. Percentages will be calculated excluding missing values. All endpoints will be calculated for the overall population and by the stratification variables listed in [Section 4.3](#) (sample sizes permitting).

To show how one treatment line moves to the next, adjacent treatment combinations will be cross-tabulated (showing frequencies), eg, treatments received in the line prior to palbociclib (T-1) will be cross-tabulated with treatment line at which palbociclib was received (T), T will be crossed by treatments received at the line following palbociclib (T+1) and T+1 will be crossed by treatments received at the second line following palbociclib (T+2.)

For each of the 4 lines, whether or not that line is still ongoing or not will be described (this excludes T-1 as that line cannot be ongoing). For those not still ongoing (ie, the line has ended), the reason for ending will be described.

Time-to-event outcomes (ie, time to treatment start, time to dose reduction, treatment duration, CCI, PFS, death) will be described using the Kaplan-Meier method. In addition to reporting median event times for these measures, time-dependent event rates (eg, proportion of patients without event at various time points from a starting point of interest) will also be reported based on lifetables derived from the Kaplan-Meier analyses. All analyses will be conducted using Stata (version 14.2 or higher) statistical software and IBM SPSS Survey Reporter.

The outlined statistical methods anticipate that the selected sample is randomly drawn from normally distributed populations. However, this study will employ a convenience sample; thus, results may not be generalizable to the entire universe of patients receiving palbociclib.

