4.3. Stratifications and Subgroups

Stratifications will be conducted to assess differences in outcomes by line of therapy, demographics, treatments clinical characteristics or ‘responders’ and ‘non-responders’ to treatment, however these will be only descriptive in nature. Responders and non-responders will be defined according to the best recorded response to palbociclib treatment.

For wave 1 countries already conducted (US, Argentina and Germany (interim)) additional stratifications included:

- Disease stage at initial diagnosis (ABC vs mBC);
- Combination partner (AI/letrozole vs fulvestrant);
- Treatment sequence (line of therapy: AI 1st line, fulvestrant 1st – 3rd line);

- Age (up to 65, greater than 65 years);
- Metastases, visceral vs. non-visceral disease.

Additional ad hoc stratifications were completed for the US 2017 analysis, as below:

- Age classification by indication (up to 65, >65);
- ECOG at palbociclib initiation for all patients and by indication;
- Palbociclib starting dose 125 mg vs not 125 mg for all patients and by indication;
- Disease progression with initial control vs without initial control;
- Visceral status (mBC only) by indication;
- Alternative classification of metastases by indication (bone metastases only, visceral disease only, bone and visceral, neither (other)).

For analysis of the wave 2 countries (Germany (core), Canada, UK, Italy, France, Belgium, Switzerland, Japan, Spain, Netherlands and Portugal), the following stratifications are requested (dependent of sample size):

- Combination partner (AI/letrozole vs fulvestrant);
- Treatment sequence (line of therapy: AI 1st line, fulvestrant 1st – 3rd line);
- Age <50, ≥50 years old;
- Age <65, ≥65 years old;
- Age <75, ≥75 years old;
- Starting dose 125 mg vs. non 125 mg.

For clinical outcomes variables only:

- Prior chemotherapy by palbociclib indication (AI/letrozole vs fulvestrant);
- Menopause status (peri- or post- menopausal);
- Disease stage at initial diagnosis (ABC vs mBC).

For treatment patterns variables only, the following stratifications may include:

- Academic vs. community institution.

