- Line of therapy that palbociclib is received (T);
- Treatments received in the line of therapy prior to palbociclib (T-1);
- Treatments received in the line of therapy post palbociclib (T+1).

Palbociclib dosing characteristics**To be abstracted directly from the medical records:**

- Palbociclib starting dose;
- Reasons for starting at a dose lower than 125 mg/day;
- Number of palbociclib dose changes;
- Details of each dose change (eg, dose increase, dose decrease, dose interruption, cycle delay);
- Date of dose change;
- Reason for dose change (eg, side effects/toxicity, lack of response);
- Status of combination partner therapy at dose change (eg, if continued or stopped).

To be derived

- Time from palbociclib initiation to first dose change;
- Duration of dose interruption;
- Duration of cycle delays.

Supportive therapies received during palbociclib treatment**To be abstracted directly from the medical records:**

- Supportive therapies received during palbociclib treatment.

Clinical Outcomes**To be abstracted directly from the medical records:**

- Initial response recorded;
- Time from palbociclib initiation to initial response;
- Frequency with which response to palbociclib was assessed;
- Proportion with complete response;
- Proportion with complete response defined by radiological evidence;
- Proportion with partial response defined by radiological evidence;
- Time from palbociclib initiation to complete response;
- Proportion with partial response;
- Time from palbociclib initiation to partial response.

To be derived

- Objective response rate defined as the proportion of patients achieving complete or partial response on palbociclib;
- Clinical benefit rate defined as the proportion of patients achieving complete or partial response, or stable disease ≥ 24 weeks on palbociclib. Stable disease will be defined as no evidence of complete or partial response, and no progression on palbociclib therapy for 24 weeks or greater;
- Proportion with stable disease ≥ 24 weeks on palbociclib;

█ [REDACTED]

- Progression free survival (if applicable) defined as the time from the start of palbociclib to the first subsequent progression or death;
- Time to death, defined as the time from the start of palbociclib to death;

█ [REDACTED]

- Progression free at 3, 6, 12, 18, 24 months defined as the proportion of patients who have no documented progression at defined time points;

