7.2.1. Definitions of Clinical Outcomes

Objective Response Rate (ORR)

Objective response rate defined as the proportion of patients achieving complete or partial response on palbociclib combination therapy.

Clinical Benefit Rate (CBR)

Clinical benefit rate is defined as the proportion of patients achieving complete or partial response, or stable disease ≥ 24 weeks on palbociclib combination therapy. Stable disease will be defined as no evidence of complete or partial response, and no progression on palbociclib therapy for 24 weeks or greater.

CCI [Redacted]

[Redacted]

Progression Free Survival (PFS)

Progression Free Survival is defined as the time from palbociclib combination treatment initiation until the earliest of (1) clinician-documented progression while on palbociclib (2) death, (3) start of a new therapy line after final palbociclib dose if the reason for discontinuation of palbociclib was disease progression, or (4) last available follow-up. Patients who did not experience a progression event (items 1, 2 and 3) will be censored at date of last available follow-up. PFS (in months) will be calculated as (first event date - palbociclib initiation date + 1)/30.4.

PFS will be analysed using a Kaplan-Meier (KM) survivor function. A table will show the survivor rate at 3 month intervals and will also show the 3 month incremental survivor rate, ie, the survivor rate from the start of that 3 month interval rather than from time zero. The median survival (if the median is reached) and a KM chart will also be shown. Time zero will be taken at the point of palbociclib initiation.

CCI [Redacted]

[Redacted]

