Treatments received when palbociclib was initiated (T)		CRF G2a	Multiple responses allowed. Each treatment will be listed separately
Treatment combination at T	Primary objective 3	CRF G2a	Mutually exclusive treatment combinations
Is that line still ongoing?	Primary objective 3	CRF G2c	
If not, what was the reason for ending?	Primary objective 3	CRF G2d	
Treatments received in the line prior to palbociclib initiation (T-1)			Multiple responses allowed. Each treatment will be listed separately
Treatment combination at (T-1)	Primary objective 3	CRF G2a	Mutually exclusive treatment combinations
Reason for ending T-1	Primary objective 3	CRF G2d	
Treatments received in the line post palbociclib initiation (T+1)			Multiple responses allowed. Each treatment will be listed separately
Treatment combination at (T+1)	Primary objective 3	CRF G2a	Mutually exclusive treatment combinations
Is that line still ongoing?	Primary objective 3	CRF G2c	
If not, what was the reason for ending?	Primary objective 3	CRF G2d	
The 2nd set of treatments received in the line post palbociclib initiation (T+2)			Multiple responses allowed. Each treatment will be listed separately

Variable	Role	Data source(s)	Operational definition
The 2nd treatment combination at (T+2)	Primary objective 3	CRF G2a	Mutually exclusive treatment combinations
Is that line still ongoing?	Primary objective 3	CRF G2c	
If not, what was the reason for ending?	Primary objective 3	CRF G2d	
Number of treatment lines received	Primary objective 3	CRF G2a	
Duration of each line of therapy	Primary objective 3	CRF G2b/c	
Duration of ongoing palbociclib treatment	Primary objective 3	CRF G2b/c	
Duration of discontinued palbociclib treatment	Primary objective 3	CRF G2b/c	
Frequency that tumour response is assessed	Primary objective 6	CRF I1a	
Date of disease progression for each regimen (if applicable)	Primary objective 6	CRF G2e	

Table 4. Palbociclib Dosing Details

Variable	Role	Data source(s)	Operational definition
Initial dose	Primary objective 4	CRF H1	
Reasons for starting dose lower than 125 mg/day	Primary objective 4	CRF H1b	
Number of dose changes	Primary objective 4	CRF H2	
Number of dose changes	Primary objective 4	CRF H3	Including zeros, ie, no changes stated in CRF H2
Any dose reductions?	Primary objective 4	CRF H3b	
Any dose increases?	Primary objective 4	CRF H3b	

Variable	Role	Data source(s)	Operational definition
Any dose interruptions?	Primary objective 4	CRF H3b	
Dose resumed	Primary objective 4	CRF H3b	

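### Time to dose reduction is planned by Kaplan-Meier with no rule for palbociclib discontinuation or death; if these are censored, the share of patients reduced by a given time is overstated

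*SAP*

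**What the plan says.** SAP 7.2 puts time to dose reduction in one list with PFS and death: "Time-to-event outcomes (ie, time to treatment start, time to dose reduction, treatment duration, CCI, PFS, death) will be described using the Kaplan-Meier method". Besides medians, it says that "time-dependent event rates (eg, proportion of patients without event at various time points from a starting point of interest) will also be reported", taken from the Kaplan-Meier life tables. The same section applies every endpoint to the whole population and to the SAP 4.3 strata where numbers allow. Those strata include aromatase inhibitor/letrozole versus fulvestrant.

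On patients without the event, protocol 8.7 says only that the Kaplan-Meier chart "will take into account those patients for which the event has not as yet occurred". The one explicit censoring rule visible in the SAP is in 7.2.1 and concerns PFS: "Patients who did not experience a progression event (items 1, 2 and 3) will be censored at date of last available follow-up". None is given for time to dose reduction, and no competing-event method is named.

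The event is not defined either. The derived dosing variable in SAP 5.5, repeated in Appendix 1 Table 4, is "Time from palbociclib initiation to first dose change". That covers increases, interruptions and cycle delays as well as reductions. Appendix 1 Table 4 separately lists a yes/no item, "Any dose reductions", which falls under the general rule in 7.2: "For categorical variables, frequency distributions (n, %) will be displayed".

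**The concern.** A patient who has permanently stopped palbociclib, or has died, cannot have a later palbociclib dose reduction. Censoring her treats her as someone whose reduction is still to come. One minus Kaplan-Meier then estimates the risk of reduction in a population where nobody stops or dies. Primary objective 4 asks about dose changes in clinical practice, and the natural reading of that is the share of actual patients who have been reduced by a given time. Those two quantities differ when stopping is common.

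At stake are the event-free percentages and median for a primary objective, and the comparison by combination partner. If one group stops sooner, its Kaplan-Meier curve departs further from the share of patients actually reduced.

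**Working it through.** The documents give no dose-reduction rate, discontinuation rate or event target, so there is no stated figure to reproduce. The calculation below is an illustration.

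**Inputs from the documents**
- Median PFS with palbociclib plus letrozole: 24.8 months (protocol section 6).
- Median PFS with palbociclib plus fulvestrant: 10.8 months (protocol section 6). SAP section 2 gives 9.2.
- Minimum follow-up: 3 months for fulvestrant, 6 months for aromatase inhibitor/letrozole (protocol 8.2.1).

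**Assumptions**
- Median PFS stands in for the median time to stopping or death.
- Hazards are constant. The reduction hazard is l = 0.02 or 0.05 per month on drug, equal in both partner groups.
- The hazard of stopping or death is m = ln 2 / median: 0.693/24.8 = 0.0279 and 0.693/10.8 = 0.0642 per month.

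**Formulas**
- One minus Kaplan-Meier, with stopping and death censored: 1 − exp(−l·t).
- Share of patients actually reduced (cumulative incidence): l/(l+m) × [1 − exp(−(l+m)·t)].

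**Worked case**: fulvestrant, l = 0.05, t = 12.
- One minus Kaplan-Meier: 1 − exp(−0.60) = 45.1%.
- Cumulative incidence: 0.05/0.1142 × [1 − exp(−1.370)] = 0.438 × 0.746 = 32.7%.

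**Results** (excess taken before rounding)

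| Partner (median PFS) | l | Month | 1 − KM | Cumulative incidence | Excess (points) |
|---|---|---|---|---|---|
| Fulvestrant (10.8) | 0.05 | 12 | 45.1% | 32.7% | 12.5 |
| Aromatase inhibitor (24.8) | 0.05 | 12 | 45.1% | 39.0% | 6.1 |
| Fulvestrant (10.8) | 0.02 | 12 | 21.3% | 15.1% | 6.2 |
| Aromatase inhibitor (24.8) | 0.02 | 12 | 21.3% | 18.2% | 3.1 |
| Fulvestrant (10.8) | 0.05 | 24 | 69.9% | 41.0% | 28.9 |
| Aromatase inhibitor (24.8) | 0.05 | 24 | 69.9% | 54.3% | 15.6 |

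With the SAP's 9.2 months for fulvestrant, the 12-month cumulative incidence at l = 0.05 is 31.0%, an excess of 14.1 points.

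The median is affected too. At l = 0.05 Kaplan-Meier gives ln 2/0.05 = 13.9 months. Yet only l/(l+m) = 0.05/0.1142 = 43.8% of fulvestrant patients would ever be reduced, so half of them never reach the event.

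**Sensitivity to timing.** Suppose all reductions fall in the first 3 months and one minus Kaplan-Meier reaches 20% to 50% by then. The excess is 0.8 to 1.8 points for the aromatase inhibitor and 1.7 to 4.0 for fulvestrant (median 10.8). If they fall in the first 6 months, it is 1.5 to 3.5 and 3.3 to 7.6 points.

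**Sensitivity to the censoring rule.** This was simulated with 400,000 patients per group. The reduction hazard was −ln(0.7)/12 = 0.0297 per month. Record review was uniform from the minimum follow-up to 30 months. Survival after stopping was exponential with an assumed mean of about 25 months (aromatase inhibitor) or 24 months (fulvestrant).

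| 12-month share reduced | Aromatase inhibitor | Fulvestrant |
|---|---|---|
| KM, stopping censored | 30.0% | 30.0% |
| KM, only death censored | 26.3% | 22.2% |
| KM, stopped patients at risk to record review | 25.8% | 21.4% |
| Cumulative incidence | 25.7% | 21.4% |

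**Sensitivity to equal hazards.** The fulvestrant excess falls below the aromatase-inhibitor excess only if the fulvestrant reduction hazard is less than about 0.32 to 0.44 of the other. This was checked at 12 and 24 months, with aromatase-inhibitor hazards that give a one-minus-Kaplan-Meier value of 30% to 50% at 12 months.

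**The case against.** The strongest reply is that the bias requires a censoring rule the SAP does not state. If the PFS rule (censor at last available follow-up) were carried over, patients who stop would stay in the risk set and the excess would nearly vanish. If only death censored, it would be under 1 point at 12 months. This stands, and it makes the bias conditional. It does not close the point: in the simulated fulvestrant case, the same data give 30.0% or 21.4% at 12 months on an unwritten choice, while SAP 7.1 asks for transparent and fully reproducible analysis.

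A second reply is that the crude n (%) for any dose reduction is also planned and lacks this upward bias. That is correct, so a reader who infers that the study's only reported share of reduced patients will be too high goes beyond the documents. The crude share is still no substitute. It has no time axis and depends on length of follow-up, whose required minimum differs by partner.

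Third, risk while remaining on treatment is a legitimate descriptive target. It is, if censoring is independent and the curve is labelled that way, but the SAP does not state that target.

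Fourth, the hazards are assumed, and patients also stop for reasons other than progression, so PFS is a rough stand-in for time on drug. This stands. The figures show a range and do not predict the study's results.

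**Conclusion.** The SAP names Kaplan-Meier for time to dose reduction without defining the event or the handling of discontinuation and death. If these are censored, one minus Kaplan-Meier overstates the share of patients reduced by a given time. Under the stated constant hazards, the 12-month excess is about 6 to 12 points for fulvestrant, and about 6 points for the aromatase inhibitor at 0.05 per month. It shrinks to about 1 to 4 points if reductions are confined to the first 3 months, and to near zero if stopped patients are kept at risk to last follow-up.

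A reader might infer that the reported share is certainly overstated, and most so with fulvestrant. The documents do not support that as fact. The censoring rule is missing, and no reduction or discontinuation rate is given by partner. A larger excess with fulvestrant is probable because its cited PFS is shorter, but that rests on broadly similar reduction hazards in the two groups.

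The point deserves action because it concerns a primary objective and a better-matched estimator is available from data already being collected.

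**What to change.** In SAP 7.2:

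1. Define the event as first palbociclib dose reduction, timed from palbociclib initiation, and keep it distinct from first dose change of any type.
2. Report its cumulative incidence (Aalen-Johansen) at 3, 6, 12, 18 and 24 months, overall and by combination partner. Treat permanent palbociclib discontinuation or death as the competing event, and censor ongoing patients at last follow-up.
3. If a Kaplan-Meier curve is also shown, label it as conditional on remaining on palbociclib.

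Kaplan-Meier can stay for PFS, death and treatment duration, and the crude n (%) can stay alongside.

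No new data are needed: SAP 5.5 already abstracts dose-change dates and treatment stop dates, and SAP 5.2 abstracts time since death. The cost is a short SAP revision and a few lines of code. The reported percentages may be lower than under Kaplan-Meier with stopping censored.
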